4.3.8 Exploratory analyses

Slope of the regression line, as defined in section 4.3.6, will be summarised (means, SD, N) for rosuvastatin treatment group only in each of the following subgroups (for only the converted LDL-C values, as described in section 4.1) to investigate the relevance of a reduction of LDL-C:

1. % change from baseline to time-weighted average during treatment in LDL-C: below and above or equal to the mean.
2. On-Treatment LDL-C (time-weighted average value):
 - below and above or equal to the mean
 - <100 mg/dL and \geq 100 mg/dL
 - <70 mg/dL and \geq 70 mg/dL
 - <70, (\geq 70- <100), and \geq 100 mg/dL
3. Loess plot of annualized rate of change in MeanMax CIMT in mm/year by % change in LDL-C and by on-treatment LDL-C (time-weighted average values).

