Although CHD and stroke have some differences in origin, atherosclerosis is a common pathophysiological basis for both. Hypertension, hyperlipidemia, smoking, diabetes mellitus, obesity, age, and sex are widely accepted as major risk factors for atherosclerosis, CHD, and ischemic stroke (NCEP 2001). To properly consider the potential hazards of dyslipidemia on the Chinese population, Chinese scholars advocate using ICVD risk to represent integrated cardiovascular risk and Chinese prevalence characteristics (Wu et al 2004). The concept of integrating the risk of CHD and ischemic stroke into a single model and then using the resulting model in clinical practice is particularly valuable in countries where stroke risk is high, as it is in China. The 2007 China Adult Dyslipidemia Management Guidelines introduced a system of risk assessment that can be employed in subjects with/without existing CHD (or a CHD risk equivalent) and with/without hypertension by counting categorical risk factors (see Appendix F). Combining this risk assessment system with blood lipid levels allows CVD risk to be comprehensively estimated, allowing stratification of risk and guiding treatment. The risk stratification scheme singles out hypertension to reflect the characteristics of Chinese clinical practice.

In the present study, classification of patient risk and definition of therapeutic goals for LDL-C will be based on the 2007 China Adult Dyslipidemia Management Guidelines. The 10-year ICVD risk is equivalent to approximately 5% to 10% when fasting LDL-C is  $\geq 120$  mg/dL (3.1 mmol/L) and  $< 160$  mg/dL (4.1 mmol/L) for subjects with only hypertension (defined as blood pressure  $\geq 140/90$  mmHg or being on antihypertensive treatment) and age as CVD risk factors, and subjects without hypertension who have 3 or more other risk factors (including age). The 10-year ICVD risk is equivalent to  $< 5\%$  when LDL-C is  $\geq 120$  mg/dL (3.1 mmol/L) and  $< 190$  mg/dL (4.9 mmol/L) for subjects without hypertension who have fewer than 3 other risk factors (including age). The above-mentioned subjects will be the target patient population for current study.

This subject population largely overlaps with the subject population in the METEOR study, and the treatment recommendation/goals are similar, following the local guideline in Chinese and NCEP ATP III in METEOR.

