4.3 Efficacy analysis

CIMT Data

In this study the CIMT data has a hierarchical (or multilevel) structure. The levels for the data are defined by 1) the study participants and 2) carotid artery sites within the participants. The repeated measure is time.

A multi-level, linear mixed-effects model will be used for the primary analysis to assess the difference in the annualized rate of change in the CIMT measurements across 12 carotid artery sites between rosuvastatin 20 mg and placebo treatment over 104 weeks. The model is specified in terms of fixed effects for randomized treatment group, time, time by treatment interaction, ICVD risk stratification (<5%/5%-10%) – based on IxRS data, carotid artery site,

age, sex, centre, and scan reader (In the unlikely event that the model does not converge it may be necessary to drop fixed effects for reader, sex and age in that order). Random effects within the model are the intercept and slope for individual subjects. Time in the model is a continuous measure and is the interval in years from date of randomization to date of CIMT measurement and its effect is linear.

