Number	Important protocol deviations / Criteria	Complete/partial data exclusion
	Inclusion Criteria	
1.	
Enrolled, for male, subject < 45 years or ≥ 70 years
 
for female, subject < 55 years or ≥ 70 years
	Complete data exclusion.
2.	
Enrolled, even though subject did not meet the criteria below:
 
Subjects with only hypertension (as defined blood pressure ≥ 140/90 mmHg or on antihypertensive treatment) and age as cardiovascular disease (CVD) risk factors and also subjects without hypertension who have 3 or more other risk factors (including age) must have:
 
 – Fasting LDL C of ≥ 120 mg/dL (3.1 mmol/L) and < 160 mg/dL (4.1 mmol/L) (Note: if a subject meets this criteria during a re-test between visit 1 and 2, this is not considered a deviation) 
Subjects without hypertension who have fewer than 3 other risk factors (including age) must have:
 
 – Fasting LDL-C of ≥ 120 mg/dL (3.1 mmol/L) and < 190 mg/dL (4.9 mmol/L) (Note: if a subject meets this criteria during a re-test between visit 1 and 2, this is not considered a deviation) 
Subjects with hypertension and age as CVD risk factors, along with at least one other risk factor, will be considered as having an important protocol deviation, regardless of fasting LDL-C values at screening.
	Complete data exclusion.

Number	Important protocol deviations / Criteria	Complete/partial data exclusion
3	
Enrolled, even though subject did not meet the criteria below:
 
TG < 500 mg/dL (5.65 mmol/L) at visit 1 (week -6)
 
(Note: if a subject meets this criteria during a re-test between visit 1 and 2, this is not considered a deviation)
	Complete data exclusion.
4	
Enrolled, even though subject did not meet the criteria below:
 
HDL cholesterol levels ≤ 60 mg/dL (1.6 mmol/L) at visit 1 (week -6)
 
(Note: if a subject meets this criteria during a re-test between visit 1 and 2, this is not considered a deviation)
	Complete data exclusion.
5	
Enrolled, even though subject did not meet the criteria below:
 
Maximum IMT ≥ 1.2 mm and < 3.5 mm in the carotid ultrasound studies conducted at both visit 2 (week -4) and visit 3 (week -2).
	Complete data exclusion.
	Exclusion criteria	

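### SAP 4.3.8: the on-treatment LDL-C groupings compare unadjusted CIMT slopes and cannot separate LDL-C reduction from baseline LDL-C and risk stratum (exploratory output; low severity)

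*SAP*

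**What the plan says.** SAP 4.3.8 states its purpose as "to investigate the relevance of a reduction of LDL-C". The outcome is the per-subject slope from SAP 4.3.6, which comes from a model with intercept, carotid site and time only. The slope "will be summarised (means, SD, N) for rosuvastatin treatment group only in each of the following subgroups", using converted LDL-C values. Three displays follow:

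- **Percent change:** the % "change from baseline to time-weighted average during treatment in LDL-C: below and above or equal to the mean".
- **Achieved level:** "On-Treatment LDL-C (time-weighted average value"), split at the mean, at 70 mg/dL, at 100 mg/dL, and into three groups at 70 and 100.
- **Plot:** "Loess plot of annualized rate of change in MeanMax CIMT in mm/year by % change in LDL-C and by on-treatment LDL-C".

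No covariate, stratification, confidence interval, test or interpretive caveat is given.

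The LDL-C entry limits depend on risk. Protocol 1.2 says "The 10-year ICVD risk is equivalent to approximately 5% to 10% when fasting LDL-C is" at least 120 and below 160 mg/dL, for subjects whose only risk factors are hypertension and age, or who have no hypertension and three or more other factors. Subjects without hypertension and with fewer than three other factors are equated with a risk below 5% and need "Fasting LDL-C of ≥ 120 mg/dL (3.1 mmol/L) and < 190 mg/dL (4.9 mmol/L"), as SAP Appendix A, no. 2 repeats. The primary model in SAP 4.3 carries "ICVD risk stratification (<5%/5%-10"%), age and sex as fixed effects. SAP 4.3.8 uses none of these.

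**The concern.** The groups in 4.3.8 are formed after randomisation and within one arm, so randomisation does not balance them. Achieved LDL-C is partly a restatement of where the subject started: two subjects with the same percent reduction can land in different on-treatment groups because their baselines differ. Because a screening LDL-C of 160 to 189 mg/dL is allowed only in the lower-risk stratum, high on-treatment groups also tend to hold more lower-risk subjects.

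If progression differs by baseline LDL-C or by risk, part of that difference would show up in the table or the on-treatment plot as an apparent LDL-C effect, or would mask one. The section's question is about reduction, and this display cannot isolate it.

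**Working it through.** The plan gives no figure to reproduce here. The sample-size assumptions are blacked out, and no LDL-C distribution, stratum split or expected reduction is stated. The check has three parts.

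**1. Arithmetic from the entry limits.** Inputs: 120 to <160 and 120 to <190 mg/dL (protocol 3.1; SAP Appendix A) and the cuts at 70 and 100 (SAP 4.3.8). Formula: on-treatment = baseline × (1 − r).

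- Common r = 45% (assumed): 120 × 0.55 = 66; 160 × 0.55 = 88; 185 × 0.55 = 101.75; 190 × 0.55 = 104.5. The higher-risk stratum spans 66 to 88 and the lower-risk stratum 66 to 104.5.
- At that r the 70 cut only separates baselines below and above 70 / 0.55 = 127, and the 100 cut those below and above 100 / 0.55 = 182.
- Reduction needed to fall below 70: 1 − 70/120 = 41.7% from 120, but 1 − 70/189 = 63.0% from 189.
- At any common r above 1 − 100/160 = 37.5%, only the lower-risk stratum can reach 100 mg/dL.

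**2. Simulation, because reductions vary.** All inputs are assumed: 30, 50 or 70% of subjects in the <5% stratum; baseline uniform within the entry limits, or truncated normal (mean 135, SD 20); mean reduction 45% (SD 5 or 12 points) or 35% (SD 20), the same in both strata; LDL-C measurement noise SD 0 or 12 mg/dL. Ranges across scenarios, upper minus lower on-treatment group:

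| Split | Baseline LDL-C (mg/dL) | Share at <5% risk (points) |
|---|---|---|
| Mean | +5 to +27 | +2 to +26 |
| 70 mg/dL | +4 to +25 | +1 to +17 |
| 100 mg/dL | +6 to +33 | +3 to +61 |

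The direction is the same in every scenario. The size of the risk imbalance is not: with the truncated normal baseline it is only about 1 to 7 points for the mean and 70 splits. The on-treatment groups also differ in true reduction, by about 4 to 31 points at the mean split, so reduction is present in the contrast but mixed with the rest.

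For the percent-change split the risk imbalance is 0 points, since reduction was set alike in both strata. The baseline difference is 0 without noise. With noise SD 12 it is 5 to 11 mg/dL in the opposite direction, which is regression to the mean.

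**3. Size against precision.** If LDL-C has no effect, the artefact from risk mix is the share difference × the difference in progression between strata. The documents give no such difference; take 0.005 mm/year.

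- Below 70 versus 100 or above, with mean reduction 40 to 50% and SD 10 to 15 points: baseline differs by about 12 to 31 mg/dL, true reduction by 23 to 36 points, and the artefact is about 0.0004 to 0.0015 mm/year.
- Extreme of the table: 0.61 × 0.005 = 0.003 mm/year. This needs a narrow spread of reductions (SD 5), where few subjects reach 100.
- Precision: the pivotal global study's interval (protocol 1.1: −0.0196 to −0.0093; 702 versus 282 subjects) gives SE = 0.0103 / 3.92 = 0.00263 and slope SD = 0.00263 / √(1/702 + 1/282) = 0.037 mm/year. With 543 randomised 1:1, about 271 are on rosuvastatin. An even split gives 1.96 × 0.0373 × √(2/135.5) = 0.0089 mm/year; a 10%/90% split gives 0.0148. This assumes the same slope SD here.

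**The case against.** Much of the opposing case stands.

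- **Reduction is also analysed directly.** 4.3.8 groups and plots by percent change, where the same percent change always means the same group. A reader might infer that the section as a whole cannot speak to LDL-C reduction. The documents do not support that: the entry-rule risk imbalance vanishes there if reductions are similar across strata. Even the on-treatment groups differ in true reduction.
- **Only the ceiling depends on risk.** The strata share the 120 mg/dL floor and overlap up to 160. The limits bind at screening, with a re-test allowed between Visits 1 and 2 (SAP Appendix A). The analysis baseline is the last value before first dose (SAP 4.1.1), normally the Visit 4 sample, so the limits are blurred in the value actually used.
- **The direction of any bias is not fixed by the entry rules.** It depends also on which stratum progresses faster, which the documents do not say.
- **The section is exploratory and descriptive.** It plans no test and makes no claim.

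Two counter-arguments do not dispose of the point. SAP 4.3.7 covers ICVD category and baseline LDL-C, but as treatment-by-subgroup interactions; it does not relate achieved LDL-C to slope. And the percent-change display is still a post-randomisation, single-arm comparison, open to confounding by adherence and to regression to the mean.

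**Conclusion.** The point holds for the on-treatment groupings and the on-treatment loess plot: they mix LDL-C reduction with baseline LDL-C and, to an uncertain degree, with risk stratum, and cannot separate them. That the groups are sorted partly by baseline follows from arithmetic. The amount of risk imbalance (about 1 to 61 points) and the slope artefact (about 0.0004 to 0.0015 mm/year between the outer groups, up to 0.003 in the extreme) rest on assumed distributions and an assumed 0.005 mm/year stratum difference. The artefact is small beside a half-width of 0.009 mm/year or wider.

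A reader might take this as a weakness in the trial's efficacy evidence. It is not: the primary and secondary conclusions come from other analyses, and the primary model already carries ICVD risk. This is a low-severity improvement to how an exploratory section answers its own question.

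**What to change.** In SAP 4.3.8, keep the raw group means and both loess plots as descriptive output, and add:

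1. A linear model in the rosuvastatin subjects of per-subject slope on time-weighted on-treatment LDL-C as a continuous term, adjusted for baseline LDL-C, ICVD stratum, age and sex, with a 95% CI. With baseline in the model, the LDL-C coefficient compares subjects who started at the same level, which is closer to the stated question.
2. The same model with percent change in LDL-C in place of the on-treatment value.
3. The source of the ICVD stratum, since SAP 4.3 uses the IxRS value and SAP 4.3.7 the eCRF value.
4. One sentence labelling every 4.3.8 result a non-randomised association.

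The cost is a paragraph and one more table; all covariates are already collected. The model does not remove confounding by adherence. The per-subject slopes also differ in precision when the number of scans differs, and a confidence interval may invite a causal reading, which is why the label matters.

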4.4 Safety variables

This section describes safety analyses to be conducted on all subjects who enter the screening phase. All analyses of safety data will present descriptive statistics. Formal statistical comparisons will not be performed.

The baseline value of each safety lab test, ECG, or physical exam endpoint is defined as the last assessment before or including Study Day 1 (i.e., day of first dose of double-blind study drug). AEs occurring on Study Day 1 (the day that the first dose of randomized study medication was taken) will be counted during the double-blind treatment period. For subjects who are randomized but do not receive any double-blind study drug, baseline is defined as the last assessment before randomization. AEs and other safety measures occurring after the last dose of randomized treatment are described in section 4.6.4.

4.4.1 Adverse events

All AEs, including SAEs, will be collected from the time of signature of the informed consent throughout the treatment period and within 10 days after last dose of study drug. AEs will be categorized according to 2 definitions:

- AEs reported during the screening phase
- Treatment Emergent AEs

Treatment emergent AEs are defined as all AEs which start on or after the first dose of study drug. An AE that was present at treatment initiation but resolved and then reappeared while the subject was on treatment, is a treatment emergent AE (regardless of the intensity of the AE when the treatment was initiated). AEs reported through 10 days after the last dose of study drug will be included in the double-blind treatment period summaries.

AEs will be reported according to the latest MedDRA version available at the time of database lock.

The selection criteria of AEs for counting are as follows:

1. Where a subject has the same AE, based on PT, reported multiple times in a single analysis period, the subject will only be counted once at the preferred terminology level in AE frequency tables.
2. When a subject has the same AE, based on PT, reported multiple times in a single analysis period, the following criteria, in order of precedence, will be used to select the event to be included in summary tables:
 - **Relationship to study medication:** Related events will take precedence over unrelated events in determining the event to include in summary tables. Missing relationship will be considered a related event.
 - **Intensity of event:** More intense events will take precedence over less intense events in determining the event to include in summary tables. Missing intensity will be considered the least intense event.
 - **Onset date:** Earlier onset date events will take precedence over later onset date events in determining the event to include in summary tables.
3. When reporting AEs by intensity, in addition to providing a summary table based on the event selection criteria detailed in item 2 above, summary tables will also be provided based on the most intense event during the analysis period - independent of relationship to study medication. For these tables, the following criteria, in order of precedence, will be used to select the event to be included in summary tables:
 - Intensity of event
 - Onset date

In summaries by SOC and PT, AEs will be sorted by decreasing frequency of each PT and SOC, within SOC, according to the “Rosuvastatin 20 mg group” subject incidence. In summaries by PT, AEs will be sorted by decreasing frequency of PT according to the “Rosuvastatin 20 mg” subject incidence.

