### **6.1 Definition of adverse events**

An AE is the development of an undesirable medical condition or the deterioration of a pre-existing medical condition following or during exposure to a pharmaceutical product, whether or not considered causally related to the product. An undesirable medical condition can be symptoms (eg, nausea, chest pain), signs (eg, tachycardia, enlarged liver) or the abnormal results of an investigation (eg, laboratory findings, electrocardiogram). In clinical studies, an AE can include an undesirable medical condition occurring at any time, including run-in or washout periods, even if no study treatment has been administered.

The term AE is used to include both serious and non-serious AEs.

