### **6.3.3 Variables**

The following variables will be collected for each AE:

- AE (verbatim)
- Date and time when the AE started and stopped
- Maximum intensity (mild, moderate, or severe)
- Whether the AE is serious or not
- Investigator causality rating against the investigational product (yes or no)
- Action taken with regard to investigational product
- AE caused subject's withdrawal from study (yes or no)
- Outcome

In addition, the following variables will be collected for SAEs:

- Date AE met criteria for serious AE
- Date investigator became aware of serious AE
- AE is serious due to
- Date of hospitalization
- Date of discharge
- Probable cause of death
- Date of death
- Autopsy performed
- Causality assessment in relation to study procedure(s)
- Description of AE

The investigator will rate the intensity of AEs using the following scale:

- mild (awareness of sign or symptom, but easily tolerated)

- moderate (discomfort sufficient to cause interference with normal activities)
- severe (incapacitating, with inability to perform normal activities)

It is important to distinguish between serious and severe AEs. Severity is a measure of intensity whereas seriousness is defined by the criteria in Section 6.2. An AE of severe intensity need not necessarily be considered serious. For example, nausea that persists for several hours may be considered severe nausea, but not an SAE unless it meets the criteria shown in Section 6.2. On the other hand, a stroke that results in only a limited degree of disability may be considered a mild stroke but would be an SAE when it satisfies the criteria shown in Section 6.2.

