4.4.2 All adverse events

The subject incidence of AEs reported during the screening phase will be summarised by all AEs, Deaths, SAEs, and withdrawal from study due to AE.

The subject incidence of treatment emergent AEs will be summarized by treatment group in the following ways:

- All AEs, (by severity)
- AEs classified as related to study drug
- Deaths
- SAEs (by severity, and excluding where the outcome was death)
- AEs leading to study discontinuation

The subject incidence of treatment emergent AEs will be summarized separately by SOC, PT and treatment group for the double-blind treatment period.

The subject incidence of the most common (reported in at least 2% of the subjects in any treatment group) treatment emergent AEs will be presented by SOC, PT and treatment group. Also, the subject incidence of treatment emergent AEs will be presented by PT, intensity and treatment group. The subject incidence of ischaemic cardiovascular AEs will also be presented by PT. Ischaemic cardiovascular AEs will be identified using key words of ‘myocardial infarction’, ‘acute coronary syndrome’, ‘unstable angina’(or angina unstable), ‘stroke’ (excluding heat stroke), ‘cerebrovascular accident’, ‘cerebral infarction’. A subject listing of all reported AEs during the screening and the double-blind treatment period will be produced.

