4.4.4 Serious adverse events

The subject incidence of treatment emergent SAEs will be presented by SOC, PT and treatment group. In addition, the subject incidence of related treatment emergent SAEs will be presented by SOC, PT, and treatment group for the safety analysis. A listing of all SAEs during screening and double-blind treatment period will be produced. If we cannot determine whether an AE is serious, it will be considered an SAE.

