4.4.6 Adverse events leading to discontinuation

Number of subjects who discontinue during the screening phase due to an AE will be listed.

Treatment emergent AEs leading to study treatment discontinuation will be summarized by SOC, PT, and treatment group for safety analysis.

In addition, a subject listing of discontinuations due to AEs will be presented for screening and double-blind treatment period.

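### SAP 4.4.1 has no rule for an adverse event ongoing at first dose that becomes serious or stops study drug on treatment; kept on its original record, it drops out of the treatment-emergent tables by arm

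*SAP*

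**What the plan says.** SAP 4.4.1 sorts adverse events into two groups, those reported in screening and those that are treatment-emergent. The main rule is "Treatment emergent AEs are defined as all AEs which start on or after the first dose of study drug". The only extension is "An AE that was present at treatment initiation but resolved and then reappeared while the subject was on treatment, is a treatment emergent AE", whatever the intensity when treatment began. Protocol 8.5.3 names the same two groups and defines neither further.

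Collection begins before treatment: "All AEs, including SAEs, will be collected from the time of signature of the informed consent". Protocol 4.1 places the screening assessments within the 6 weeks before randomization.

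The by-arm outputs are tied to the treatment-emergent class:

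- SAP 4.4.2: "The subject incidence of treatment emergent AEs will be summarized by treatment group in the following ways", with rows for related events, deaths, SAEs and discontinuations.
- SAP 4.4.4: "The subject incidence of treatment emergent SAEs will be presented by SOC, PT and treatment group".
- SAP 4.4.5: the related-event tables carry the same restriction.
- SAP 4.4.6: "Treatment emergent AEs leading to study treatment discontinuation will be summarized by SOC, PT, and treatment group for safety analysis".
- SAP 4.4.7: the listing for subjects with marked CK, liver, creatinine or urine findings is also limited to treatment-emergent events.

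Protocol 6.3.3 lists, for each event, a start and stop date, one maximum intensity, the action taken with study drug and whether the event caused withdrawal. SAEs carry a further field, "Date AE met criteria for serious AE".

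**The concern.** The rule covers an event present at first dose only if it goes away and comes back. It says nothing of one that persists and then turns serious or causes study drug to be stopped. The separate seriousness date in protocol 6.3.3 shows that an event is expected to be able to become serious after it began, on the same record. On a start-date rule, such an event stays in the screening class however it ends.

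SAEs and AEs leading to discontinuation are named safety outcome measures in protocol 2.3, and the by-arm tables are where a reader compares the arms on them. There is also a reconciliation problem. The disposition table (SAP 4.2.1) and the all-deaths summary (SAP 4.4.3) do not filter on onset, whereas the AE-discontinuation table and the treatment-emergent deaths row do. The same subject could be in one and not the other.

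Elsewhere the SAP settles doubt towards counting: a missing relationship is treated as related (4.4.1), undeterminable seriousness as serious (4.4.4), and a fully missing start date is set to first dose (4.6.5). This gap runs the other way.

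**Working it through.** There is no figure in the plan to reproduce, so the check is to follow one case through the rules.

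**Case.** An event starts in screening (say muscle pain in week -3), does not resolve, and is ongoing at first dose. On treatment (say week 8) it meets a serious criterion and study drug is stopped. The site keeps one record.

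**Classification under SAP 4.4.1**

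1. Start on or after first dose? No; the recorded start is in screening.
2. Resolved and then reappeared on treatment? No; it never resolved.
3. Any other route? None in SAP 4.4.1 or protocol 8.5.3. SAP 4.6.4 also works on onset date and adds no route. The imputation in SAP 4.6.5 applies only when the start date is wholly missing.

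The event is therefore not treatment-emergent.

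**Where it appears**

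| Output | Included? |
|---|---|
| Treatment-emergent AE tables by arm, 4.4.2 | No |
| SAE tables by arm, 4.4.4 | No |
| Related-event tables, 4.4.5 | No |
| AE-discontinuation table, 4.4.6 | No |
| Listing for marked laboratory findings, 4.4.7 | No |
| Screening-phase summary, 4.4.2 (has SAE and withdrawal rows) | Yes |
| Listings of AEs, SAEs and AE discontinuations, 4.4.2, 4.4.4, 4.4.6 | Yes |
| All-deaths summary, 4.4.3 | Yes, if fatal |
| Disposition by arm, 4.2.1 | Yes, if the subject left the study |

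**Variants of the case**

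- *Worsens in intensity only.* Protocol 6.1 includes in the AE definition "the deterioration of a pre-existing medical condition following or during exposure to a pharmaceutical product". A site that enters the deterioration as a new event gives it an on-treatment start, and it is captured. A site that updates the existing record does not. With one maximum intensity and no date of change, the analyst cannot tell the two apart afterwards.
- *Condition predates consent.* It is medical history, so its deterioration on drug is an event starting on treatment, and it is captured.
- *Start date wholly missing.* It is imputed to first dose, and it is captured.

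**Can the missing outcomes be derived?** Seriousness: yes, by comparing the date the event met serious criteria with the first and last dose dates. Drug stop: yes, from action taken together with the last dose date. Neither needs new data.

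**Size.** The gap is limited to events with onset between consent and first dose that are still present at first dose and then take one of these two turns. The documents give no rate for any of these steps, so no count can be derived.

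**The case against.** The best reply is that the protocol already makes on-drug deterioration an event of its own. Under 6.1 it meets the AE definition. Under 6.3.6, new or aggravated physical findings are reported as events, as are mandated laboratory values that deteriorate from baseline and are serious or cause drug stop. The counting rules in SAP 4.4.1 allow for the same preferred term reported more than once. The muscle and liver outcomes of most interest have other routes: Appendix D requires myopathy always to be recorded as an AE, Appendix C reports confirmed or unresolved potential Hy's Law cases as SAEs under their own terms, and SAP 4.5.2 summarises ALT, CK and creatinine elevations by arm whatever the AE onset. Visit 1 exclusions on liver tests and CK make ongoing abnormalities of that kind unlikely.

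Much of this stands. A reader might infer that on-drug worsening is missing from every safety table; the documents do not support that, because new records are captured and the listings and onset-free summaries remain. A reader might also infer a bias towards no difference between arms. That is not shown either: losing a similar share of events in both arms shrinks the risk difference but leaves the ratio unchanged, the direction depends on how often this happens in each arm, and safety is descriptive with no formal tests.

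What the reply does not do is close the gap. No passage tells sites to open a new record when an ongoing event becomes serious or stops drug, the fields in 6.3.3 fit a single evolving record, and listings are not incidence by arm.

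**Conclusion.** The definition is incomplete on two outcomes: an event ongoing at first dose that becomes serious on treatment, and one that leads to stopping study drug. The conclusion rests on one assumption, that the site kept the event on its original record. The eCRF completion rules are not in the documents, so this cannot be confirmed. Intensity-only worsening is a weaker limb, since it turns wholly on recording practice and cannot be recovered from the fields collected.

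The number affected is unknown and may be small, given a screening period of about 6 weeks. The point is worth acting on because it is cheap to close before unblinding and concerns named safety outcomes, not because a distortion of the safety comparison has been demonstrated.

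**What to change.** In SAP 4.4.1, also count as treatment-emergent any AE with onset before first dose that, from first dose to 10 days after last dose:

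- (a) first meets a serious criterion, using the date already collected; or
- (b) leads to stopping investigational product, using action taken already collected together with the last dose date.

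Apply this to SAP 4.4.2 and 4.4.4 to 4.4.7. Align the onset wording in 4.6.4 so that it does not exclude these events, and do not count their on-treatment seriousness or drug stop in the screening-phase summary.

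A new eCRF instruction for intensity changes is not proposed. The study was due to end by 1Q 2019 and the SAP was last amended on 05Mar2019, so it would come too late to change how events were entered.

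The cost is SAP wording and a little programming, with no new data. AE counts would be slightly higher. Protocol 8.1 requires final SAP amendments before unblinding, so the change should be made by then.
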